#### Study procedure - evaluation

##### Clinical evaluations

At the first baseline visit, a thorough medical history will be taken both by using a patient interview as well as by using past medical records from the electronic health records. A list of current medications is made, where all currently taken medications should be included, both prescription and over-the-counter medicine, as well as medicine taken within the last 30 days. The patients PDAI score must be recorded.

The physical examination will include a measurement of vital signs (blood pressure, pulse, temperature, respiratory frequency), as well as cardiopulmonary, gastrointestinal and gross neurological examination. Current weight, height, BMI (body mass index), ASA score, performance status.

Subsequent visits will include a short update of the medical history, an update of the PDAI as well recording any adverse reactions during the study period. A clinical symptom-directed examination is done if the investigator deems this necessary.

All data is recorded in Easytrial by direct entry, using autoquery to minimize faulty data entry.

##### Laboratory evaluations

The following blood sample analyses will be taken to monitor signs of inflammation as well as adverse reactions to the medication.

Type of vial:	Clinical biochemistry test:	Amount of samples
EDTA	Hemoglobin; B Leukocytes; B Thrombocytes; B Leukocyte type;	2 blood samples per patient taken at baseline (Day 1) and 7 days after end of treatment
Heparin	Creatinine; P Potassium; P HCG (in females); P Alkaline phosphatase; P	2 blood samples per patient taken at baseline (Day 1) and 7 days after end of treatment
Li-Heparin	Sodium; P Bilirubin; P ALAT; P Amylase; P Lactate dehydrogenase; P	2 blood samples per patient taken at baseline (Day 1) and 7 days after end of treatment

	CRP; P	
--	--------	--

Blood samples will be analyzed by the clinical biochemistry department at the Sjælland University Hospital Køge. Per vial between 7-10 ml of blood are drawn, with 3 vials drawn both at baseline (Day 0) and 7 days after treatment. In total 6 vials of blood are drawn, with a maximum of 60 ml of blood.

### **Control endoscopy Phase I and II**

After seven days, endoscopy of the pouch will be performed again after application of a cleansing enema by the patient 1 hour before the examination. The pouch mucosa will be visually assessed and biopsies of the pouch mucosa taken to assess change in the mucosa according to the PDAI, as well as to examine change in the microbial diversity.

The endoscopy of the pouch will be performed by a trained specialist surgeon in the outpatient endoscopy clinic.

### **Special assays or procedures**

#### **Histology**

Two biopsies of 2 mm in size each will be taken for assessment of inflammation of the mucosa, according to the PDAI. Biopsies will be fixed in a 4% neutral buffered formaldehyde ('formalin') solution. Biopsy samples will be prepared in sections of FFP (formalin fixed paraffin) wax-embedded tissue, for histology with routine HE (hematoxylin/eosin)-staining. A trained pathologist will review the samples, without prior knowledge of the patient's clinical or treatment status.

Biopsies are reported descriptively and using the PDAI. They will assess the quantity of acute and chronic inflammation, presence of crypt abscesses, erosions and ulcers as well as loss of villous height, granulomas and dysplasia. Chronic inflammatory changes will be distinguished from true pouchitis, as the mucosa of the healthy pouch undergoes adaptive changes after surgery. These changes, which are also frequently described as 'colonic metaplasia' include villous atrophy, crypt hyperplasia, infiltration of the lamina propria of mononuclear cells, eosinophils and histiocytes (68).

#### **Microbial diversity**

Two biopsies will be taken for assessment of the microbial diversity of the mucosa. It has previously been shown that up to 60-80% of pouch microbiota cannot be cultured (30). Furthermore, there is a difference in analyzing the luminal microbiota (fecal samples) or mucosa-adherent microbiota (mucosal samples). It is assumed that the mucosal microbiota is more relevant in the pathogenesis of IBD, and we will focus on these in our study (31). Therefore, we will take mucosal biopsies, which will be analyzed by 16S rRNA sequencing.

#### **Safety assessments and adverse events or reactions**

An adverse event (AE) is any untoward medical occurrence in a patient or clinical investigation subject that has been given a pharmaceutical product, regardless of its causal relationship to the study treatment. This can be an abnormal laboratory finding, a symptom or disease coincident in time with the use of the investigational medicinal product.

During and after administration of GM-CSF, fosfomycin and metronidazole, any adverse events or intercurrent illnesses will be reported. Patients who have known allergy to GM-CSF, fosfomycin and or metronidazole are excluded from study participation. The administration of the study drug combination will be in the presence of a medical doctor, the principal investigator. Patients will be observed in the endoscopy unit for at least 1 hour after the first administration of the drug. In case of the occurrence of

an adverse event or serious adverse event, monitoring and further treatment steps will be taken according to the type and severity of reaction.

The severity of the AE will be assessed using the following grading system:

- Mild: requires minimal or no treatment, does not interfere with the patient's daily activities
- Moderate: low level of inconvenience or concern with therapeutic measures, some interference with the patient's daily activities
- Severe: interrupts a patient's daily activities, may require systemic drug therapy or other treatment, and is usually incapacitating
- Life threatening: places the patient at immediate risk of death from the reaction as it occurs

Changes in the severity of the AE will be documented.

All AEs, including both local and systemic events not meeting the criteria for 'serious adverse events' will be captured on the appropriate form for recording AEs. We will collect information on

- Description of the event
- Time of onset
- Clinician's assessment of the severity
- Relationship to the study product
- Time of resolution/stabilization of the event

Any medical condition that the patient has at baseline (time of inclusion in the study), will not be considered or reported as an AE. If an existing medical condition worsens during the study, it will be recorded as an AE.

### **Adverse reactions**

An adverse reaction is an adverse event where there is a reasonable possibility of a causal relationship between the investigative medicinal product (IMP) and an adverse event. The assessment of causality can be done using the WHO-UMC Case Causality Assessment, which uses certain criteria to determine if causality is plausible. Causality can hereafter be

- Certain
- Probable/likely
- Possible
- Unlikely
- Conditional/Unclassified
- Unassessable/Unclassifiable

We will attempt to assess the relationship of the AE to the study drug. All AEs will be reported, using the following guidelines:

- Related: reasonable possibility that the study drug caused the AE or evidence to suggest a causal relationship between study drug and the AE. The adverse event can thereafter be classified as an adverse reaction (AR).
- Not related: no reasonable possibility that the administration of the study drug caused the event

### **Serious adverse events or reactions**

An AE or AR is considered serious when resulting in death, is life-threatening, results in hospitalization or prolongation of existing hospitalization, causes persistent or significant incapacity or substantial disruption of the patient's daily activity or causes a congenital anomaly or birth defect, and other adverse events that according to the investigator's judgement are medically significant. A medical event that

requires surgery or medical intervention to prevent one of these outcomes is also considered a serious AE or AR. All SAE (Serious adverse events) and SAR (Serious adverse reactions) will be recorded on the appropriate form, and followed through resolution by the investigator as well as reviewed and evaluated.

All SAE and SAR will be registered and reported to the sponsor by the investigator within 24 hours after the event has been recorded by e-mail. All adverse reactions will be reported to the Danish Medicines Agency and the local Ethics Committee in an annual report with a report on patient safety of the trial. All SAR will be reported in an annual report together with a report on patient safety to the Danish Medicines Agency. All SAE and SAR will be evaluated by the investigator according to the known possible adverse reactions reported in the product summary (see below) if they are a possible SUSAR (Suspected unexpected serious adverse reaction).

As there are no previous data on the administration of GM-CSF, fosfomycin and metronidazole in the pouch, there are no data on expected serious adverse events or reactions in the reference safety information of the Investigator's Brochure of GM-CSF. Therefore, all SAE and possible SAR are considered to be related to the investigational medicinal product and will be reported as SUSAR.

The investigators are responsible for reporting all lethal or life-threatening SUSAR to the Danish Medicines Agency and the regional Ethical Committee as soon as possible and no later than 7 days after knowledge of such reaction has been received. No later than 8 days after the reporting, the Danish Medicines Agency will be informed of the follow-up. All other SUSAR will be reported to the Danish Medicines Agency and the regional Ethics Committee no later than 15 days after knowledge of the reaction has been received by the sponsor and the investigators. In these situations, the patient will be followed until the reaction has terminated either via the outpatient clinic at the hospital or via contact with the sponsor or the investigators.

#### **Life-threatening adverse events**

An adverse event is considered as life threatening if, in the investigator's opinion, the occurrence places the patient at immediate risk of death.

#### **Unexpected adverse event**

If an adverse event is not listed in the investigator brochure, it is considered 'unexpected'.

We will immediately report to the sponsor any unexpected serious adverse events, drug-related or not, including an assessment of whether we suspect the drug as the causative agent.

Adverse events and reactions will be monitored and followed up until end of the study and/or resolution of the adverse event or reaction, or until the adverse event or reaction is considered chronic.

The summary of the product characteristics and or investigator's brochure of GM-CSF, fosfomycin and metronidazole will function as a reference document for the evaluation of adverse effects. We will monitor adverse events and reactions from the day of the intervention in Phase I and II until respectively day 30 and 37. Monitoring will depend on asking patients if they have developed known adverse events or reactions as seen in Appendix 8, and self-reporting by the patient. Patients will have the possibility to contact the investigator by telephone during the duration of the trial, to report any adverse event or reaction. Patients will be encouraged to contact the relevant authority and initiate relevant help in case of serious acute adverse events or reactions.

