### GM-CSF

Knowledge about adverse reactions after GM-CSF is mainly based on i.v. (intravenous), i.m. (intramuscular) and s.c. (subcutaneous) administration. We suspect that application of a low dose of 50 µg to the mucosa of the pouch will result in less frequent systemic adverse reactions.

Fever is the most common adverse effect, often accompanied by myalgia and malaise, and occurs in more than 20% of recipients of the conventional systemic dose of 250 µg. For GM-CSF application, the following known and usual side effects (1-10%) and known and non-usual side effects (0.1-1%) will not be registered as adverse reactions: fever, malaise, myalgia, abdominal pain, diarrhea, rash, chest pain, weight loss, nausea and vomiting, peripheral edema, dyspnea, hypoxemia, hypotension, tachycardia, flushing, metabolic disease, hyperbilirubinemia, cardiac dysrhythmia and pharyngitis (65).

Effects are more common when GM-CSF is administered intravenously and with doses greater than 3 µg/kg. High doses (20 µg/kg/day) of GM-CSF have been reported to cause a generalized capillary leak syndrome (4,66). In our study, only 50 µg are applied locally in the pouch.

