### **Drug combination risks**

One recent study tested intraperitoneal administration of GM-CSF for peritonitis on patients undergoing laparoscopic appendectomy for uncomplicated appendicitis in 14 otherwise healthy male individuals. In this Phase II trial, 50 µg of molgramostim was administered into the peritoneal cavity directly after appendectomy, along with 4 g of fosfomycin and 1 g of metronidazole.

No serious adverse events or complications occurred. Adverse events included dizziness, diarrhea, hypotension, no flatus and discomfort when breathing deeply. However, it was not possible to determine if these occurred due to the study drug combination, or were complications related to the anesthesia,

surgery or appendicitis. It is also unclear if these adverse events, if related to the study drug, were a reaction to the GM-CSF, fosfomycin or metronidazole (67).

We hypothesize therefore, that application of the study drug combination is safe in the pouch. We will also be using a lower dosage of fosfomycin and metronidazole.

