## Appendix 2 – Study schedules

### Phase I Study Schedule

		Follow-Up Schedule			
Procedures		Screening Day 0	Baseline Day 1	Follow-up Day 7	Follow-up Day 30
Signed Consent Form		X	X		
Assessment of Eligibility Criteria		X	X		
Review of Medical History		X	X		
Review of Concomitant Medications		X	X	X	X
Application of study drug			X		
Physical Examination	Complete	X		X	
	Symptom-Directed		X		
	Vital Signs		X	X	
Assessment of Adverse reactions			X	X	X
Clinical Laboratory	Chemistry	X		X	
	Hematology	X		X	
Histology	Endoscopy with Biopsies		X	X	
Microbiology			X	X	

Phase II Study Schedule

				Follow-Up Schedule		
Procedures		Screening Day 0	Baseline Day 1	Hospital administration Day 2-7	Follow-up Day 14	Follow-Up Day 37 (1 month after treatment)
Signed Consent Form		X	X			
Assessment of Eligibility Criteria		X	X			
Review of Medical History		X	X			
Review of Concomitant Medications		X	X		X	X
Application of study drug as enema			X	X		
Physical Examination	Complete	X			X	
	Symptom-Directed		X			
	Vital Signs		X		X	
Assessment of Adverse reactions			X	X	X	X
Clinical Laboratory	Chemistry	X			X	
	Hematology	X			X	
Histology	Endoscopy with Biopsies		X		X	
Microbiology			X		X	

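### No vital signs are scheduled between Day 1 and Day 7 (Phase I) or Day 14 (Phase II), so transient, symptom-free falls in blood pressure or saturation after dosing may go undetected

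*Protocol*

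**What the plan says.** Chapter 7 of the protocol, under Unexpected adverse event, describes ascertainment as follows: "Monitoring will depend on asking patients if they have developed known adverse events or reactions as seen in Appendix 8". The same sentence adds self-report as a second source. The GM-CSF column of Appendix 8 has 20 tick-box items. Chapter 3 (GM-CSF) lists the same effects, ending with "dyspnea, hypoxemia, hypotension, tachycardia, flushing, metabolic disease, hyperbilirubinemia, cardiac dysrhythmia and pharyngitis".

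The Phase I primary outcome in chapter 3 is adverse reactions as seen in Appendix 8. The GM-CSF section of that chapter nevertheless states that "known and non-usual side effects (0.1-1%) will not be registered as adverse reactions: fever, malaise, myalgia, abdominal pain" and the rest of the list.

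Appendix 2 marks vital signs on Day 1 and Day 7 in Phase I, and on Day 1 and Day 14 in Phase II. The Phase II column for hospital dosing on Days 2-7 has no vital-signs mark, but the row "Assessment of Adverse reactions" is marked there.

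Chapter 7 also provides that "The administration of the study drug combination will be in the presence of a medical doctor, the principal investigator" and that "Patients will be observed in the endoscopy unit for at least 1 hour after the first administration of the drug". It does not say what is measured during that hour.

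**The concern.** Questioning works for nausea or myalgia. It does not work for blood pressure or oxygen saturation, and only partly for heart rate and rhythm. If these are not measured near the dose, a blank box on the form cannot separate a reaction that did not happen from one that nobody looked for.

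This matters because chapter 7 says there are no previous data on giving this combination in the pouch, because Phase I has six patients with safety as its primary outcome, and because Phase II moves to seven daily doses. Of the earlier intraperitoneal trial of the combination, the protocol says: "Adverse events included dizziness, diarrhea, hypotension, no flatus and discomfort when breathing deeply". Hypotension is therefore a sign the protocol has reason to look for, although that trial could not attribute it to the drug.

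**Working it through.** The protocol states no figure to reproduce. The check sets the schedule against the list and counts.

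**1. When vital signs are scheduled (Appendix 2)**

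| | Phase I | Phase II |
|---|---|---|
| Vital signs marked | Days 1, 7 | Days 1, 14 |
| Adverse-reaction assessment marked | Days 1, 7, 30 | Days 1, 2-7, 14, 37 |
| Days between sets | Days 2-6 = 5 | Days 2-13 = 12 |
| Doses on those days, per patient | 0 | 6 of 7 |
| Last dose to next set | 7 - 1 = 6 days | 14 - 7 = 7 days |

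Planned Phase II doses on days without a mark: 12 x 6 = 72.

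**2. Is the Day 1 set before or after the dose?** Appendix 2 does not say. Chapter 4 lists the Day 1 clinical examination before the endoscopy and dose in both phases, and chapter 7 (Clinical evaluations) puts vital signs in the baseline examination. The natural reading is pre-dose, but it is not stated. If that reading is right, the 6 Phase I doses and the 12 Phase II Day 1 doses also have no scheduled post-dose reading, and the Phase II total becomes 72 + 12 = 84.

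**3. Which Appendix 8 items are affected?** Of the 20 GM-CSF items:
- Hypotension and hypoxemia cannot be reported by a patient and would be found by bedside readings: 2/20 = 10%.
- Tachycardia and cardiac dysrhythmia can be felt in part.
- Fever can be noticed or measured.
- Hyperbilirubinemia is a laboratory value, and chapter 7 already schedules bilirubin at follow-up.
- Metabolic disease is not detectable from vital signs.

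**4. Is there a place to record a post-dose reading?** Chapter 9 names Appendices 3-6 and 8 as CRFs. Appendix 4, the Day 1 dosing form, has free text for complications but no vital-signs field. Appendix 8 has fields for blood pressure, pulse, temperature, saturation and respiratory rate, but is headed for Days 7, 14, 30 and 37. None of the named forms is headed for Days 2-7. The vital signs defined in chapter 7 omit saturation, although the examination forms after Appendices 3 and 8 have a field for it.

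**5. What would a clean result mean?** If all six Phase I patients were measured and none had the sign, the one-sided 95% upper limit for its incidence would be 1 - 0.05^(1/6) = 39.3%. Even that wide limit assumes six measured patients.

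For scale, chapter 3 quotes bands of 0.1% to 10% for the listed effects, mainly from systemic use. If such an incidence p applied per patient, the chance of at least one case is 1 - (1 - p)^n: 0.6% to 46.9% for n = 6, and 1.2% to 71.8% for n = 12. These are chances of occurrence. The documents give nothing from which a probability of missing a case can be computed.

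**The case against.** A reader might infer that these reactions will be recorded as absent. The documents do not support that. A doctor is present at administration, patients are observed for at least an hour after the first dose, adverse reactions are assessed on each Day 2-7 visit, patients can self-report, and follow-up brings vital signs, examination and blood tests. Abnormal laboratory findings count as adverse events. What remains exposed is the transient, symptom-free change. The listed safeguards do not fully cover it: the observation hour applies to the first dose only and names no parameter, and the follow-up readings come 6 or 7 days after the last dose.

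A reader might also infer that the gap distorts the decision to start Phase II. Chapter 4 ties that decision to the absence of serious events, and a symptom-free reading would not normally be serious. It could inform the general safety and feasibility assessment in chapters 4 and 10, but no more than that.

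The strongest objection is that chapter 3 bars the listed effects from registration as adverse reactions, so better measurement alone might leave the primary outcome unchanged. That stands. However, chapter 7 requires all adverse events to be captured and reported, so the readings still matter for the safety data.

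The hypotension in the earlier trial is limited as a precedent. It followed laparoscopic appendectomy with 4 g fosfomycin and 1 g metronidazole, ten times the amounts here (4 g/400 mg; 1 g/100 mg), and the protocol says the cause could not be determined. Finally, the content of Appendices 10, 14 and 15 is not visible in the copy reviewed, and chapter 6 refers to separate administration instructions, so readings may be specified there.

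**Conclusion.** The point holds as a gap in the measurement schedule. Appendix 2 has no vital signs between Day 1 and Day 7 or 14, and this covers 72 planned Phase II doses given in hospital. The larger count of 84, and the statement that Phase I has no post-dose reading before Day 7, rest on the Day 1 set being pre-dose, which chapter 4 suggests but does not state. Two of the 20 GM-CSF items, hypotension and hypoxemia, are both unreportable and recoverable by bedside readings; tachycardia and dysrhythmia are partly affected.

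The consequence is limited to transient, symptom-free changes that may go undetected, so that their absence from the data would be weak evidence of safety. Separately, the chapter 3 non-registration rule conflicts with the Phase I outcome defined through Appendix 8. Until the two are reconciled, measured findings may not reach that outcome. All of this assumes that no document outside the copy reviewed already schedules these readings.

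**What to change.** - **Appendix 2:** add a post-dose set of the vital signs already defined in chapter 7, plus the saturation already on the examination forms, within the existing observation hour on Day 1 and at each Day 2-7 hospital visit. State whether the existing Day 1 set is before the dose.
- **CRF:** add one line for these readings, usable on Day 1 and on Days 2-7.
- **Chapter 7 and Appendix 8:** state that hypotension, hypoxemia, tachycardia and fever are completed from the readings, and hyperbilirubinemia from the follow-up laboratory result, rather than from questioning alone.
- **Chapter 3:** reconcile the rule that listed effects are not registered as adverse reactions with the Phase I outcome in the same chapter and with the capture and reporting of all adverse events in chapter 7, so that these findings enter the safety outcome.

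The cost is 6 sets of readings in Phase I and 12 x 7 = 84 in Phase II, all while the patient is already in hospital: a few minutes per dosing visit and one CRF line. No dose or treatment rule changes.

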## 8. Statistical considerations

We plan to include 6 patients in the Phase I study to test tolerability, and 12 patients in the Phase II study to test effectiveness of the treatment. The trial will end with the last visit of the last patient (Day 37 of the last patient). This is a safety and clinical proof-of concept intervention study, and we are, to the best of our knowledge, the first group to look into local treatment with GM-CSF and antibiotics of biofilm in patients with pouchitis after IPAA for ulcerative colitis. We expect this number of patients to be sufficient to provide the necessary experience in implementing the technique and form a basis for future studies, including future sample size calculation. This is based on calculations on number of patients required to achieve statistical significance of paired before-and-after comparisons by non-parametric tests. To achieve statistical significance at 1% level in Phase II, 9 patients are needed. As there is a risk of patients withdrawing from the trial prematurely or not receiving all interventions, we aim to include 3 additional patients.

Our primary objective is to test for adverse events or reactions in Phase I and a significant change in PDAI in Phase II, defined by a decrease of 3 points. Differences pre- and post-treatment will be described by means and standard deviations, or median and range when appropriate, and will be analyzed by the appropriate statistical tests. All patients described in chapter 5 as 'Completed test persons' will be included in the statistical analysis.

Microbial diversity changes will be analyzed using PERMANOVA (permutational analysis of variance). Other secondary objectives like change in WBC and CRP will be analyzed using the appropriate statistical tests.

Data will be analyzed using non-parametric or parametric statistics depending on the distribution of the data. P-values  $\leq 0.05$  are considered significant. Correction for multiple comparisons will be performed if needed. Descriptive statistics will be used for baseline characteristics.

Missing data will be handled depending on the type of data missing. If missing data results in a patient not being able to be defined as a 'Completed test person' (Chapter 5), the patient is excluded from the trial and a new patient will be recruited. If individual results are missing (e.g. laboratory values), the last known values will be used for analysis.

Due to the small number of patients enrolled and only one open treatment arm, there are no scheduled interim statistical analyses. Instead, a continuous evaluation of adverse reactions and serious adverse reactions is made according to the guidelines by the Danish Medicines Agency and Ethics Committee. The sponsor will be involved promptly in case of a SAR or SUSAR, and the trial may be halted or terminated at the least suspicion of impacted patient safety.

All deviations from the original statistical analysis plan will be provided in the final clinical study report.

We will use the program R statistics 3.6.2. to analyze all statistical data.

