## 2. Background and scientific rationale

The surgical procedure of choice for patients with therapy-resistant UC (ulcerative colitis) is proctocolectomy with IPAA (ileal pouch anal anastomosis) (1). The intent of the procedure is a definitive cure of the disease and reduction of the risk of developing malignancy while preserving continence.

Pouchitis, inflammation of the mucosa of the ileoanal reservoir, is one of the most common complications after IPAA. (2) Symptoms of pouchitis include hematochezia, increased stool frequency and urgency, abdominal cramping, pain, nausea, incontinence and fever, as well as extraintestinal manifestations. Endoscopy typically shows the mucosa to be erythematous, with friability and loss of vascular patterns. Histology shows signs of inflammation and extravasation of red blood cells in the lamina propria. Interestingly, the incidence of pouchitis is about 10 times lower in patients after IPAA in FAP (Familial adenomatous polyposis) (7). Various scoring systems have been developed to assess the severity of inflammation in pouchitis, of which the PDAI (Pouchitis Disease Activity Index) is the most common. It assesses clinical, endoscopic and histological features (8) (see Table 1 in Appendix 1).

Pouchitis can be further categorized into acute and chronic pouchitis.

- Acute pouchitis – duration <4 weeks
- Chronic pouchitis – duration >4 weeks despite therapy

The incidence of acute pouchitis has been reported to be up to 50% at 5 years and there is no official consensus on treatment (9,10).

Treatment includes oral antibiotics, most often with metronidazole and/or ciprofloxacin. The standard treatment at Zealand University Hospital for acute pouchitis consists of a 10-day treatment period with oral metronidazole or ciprofloxacin. Metronidazole, while effective, can cause nerve damage after prolonged use in high doses. As patients often experience repeated flare-ups of acute pouchitis or chronic pouchitis, this risk increases due to repeated and lengthy use (11).

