#### **Screening**

Recruitment of patients will be done consecutively in the outpatient clinic. All patients with a flare up of acute pouchitis will receive information about the trial in the outpatient clinic and referred to the principal investigator. The treating physician, an experienced gastroenterologist on pouchitis, will only inform the patient that a clinical trial is ongoing, and give written information on the trial to the patient. If the patient is interested in hearing more about the trial, he or she will be offered a consultation with the principal investigator. Initial information and a consultation with the principal investigator therefore takes place before informed written consent. The identity of the patient and basic demographic information is given to the investigator after verbal consent from the patient in the outpatient clinic.

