### **Standard of care**

Patients will not be experiencing any delay in traditional treatment of pouchitis when participating in this trial. Current waiting times on outpatient clinic visits and endoscopy of the pouch, result in start of antibiotic treatment after a few weeks. If included in the trial, patients receive endoscopy and the trial medicine within two weeks, after which standard treatment of oral metronidazole or ciprofloxacin is

administered. Patients participating in the trial will therefore not be suffering symptoms of pouchitis longer than patients not participating in the trial, and no established effective intervention is withheld.

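### Section 8 says Phase II will test effectiveness, but its uncontrolled before-and-after comparison can only show change from baseline

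*Protocol*

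**What the plan says.** Protocol section 8 gives the purpose of Phase II as "12 patients in the Phase II study to test effectiveness of the treatment". It rests the number on "paired before-and-after comparisons by non-parametric tests" and continues: "To achieve statistical significance at 1% level in Phase II, 9 patients are needed". For withdrawals, "we aim to include 3 additional patients". The Phase II objective is a significant change in PDAI, defined by a fall of 3 points. P-values up to 0.05 "are considered significant. Correction for multiple comparisons will be performed if needed". The same section says the trial should support future sample-size calculation.

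There is one open treatment arm (section 3, Bias; section 4), and no control or benchmark rate is given. The Bias paragraph deals with blinding only. On recruitment, section 7 (Screening) says "All patients with a flare up of acute pouchitis will receive information about the trial". Section 2 defines "Acute pouchitis – duration <4 weeks", and pairs it with chronic pouchitis as lasting more than 4 weeks despite therapy. Section 10 (Standard of care) says that, once included, "patients receive endoscopy and the trial medicine within two weeks". The Phase II control endoscopy is on Day 14, with a window of Day 13 to 16.

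Section 10 (Choice of study design) says the results cannot definitively answer questions of efficacy. Section 10 (Post-trial access) foresees a larger, potentially placebo-controlled trial.

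**The concern.** The null hypothesis of a paired before-and-after test is that PDAI does not change between the two assessments. That is the same as no treatment effect only if PDAI would have stayed level without treatment, and the protocol nowhere argues this. Patients are approached when symptoms have flared, so some may improve by natural course or by regression to the mean. The test cannot tell such improvement from a drug effect.

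Two things are at stake. A significant result could be read as evidence of effectiveness, because section 8 uses that word. And the observed change is meant to feed the next trial's sample size. In a placebo-controlled trial the natural course occurs in both arms, so an effect that includes it would make that trial too small.

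**Working it through.** **The plan's own figure.** If every patient improves, the smallest two-sided p-value of a sign or signed-rank test is 2 × (1/2)^n:

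- n = 7: 0.0156
- n = 8: 0.0078
- n = 9: 0.0039

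Eight is therefore the bare minimum for two-sided 1%, and at 9 the signed-rank test also tolerates one adverse change of the smallest rank (p = 0.0078). The stated 9 is consistent with this, and 9 + 3 = 12. The reconstruction needs no effect size, SD, power or untreated rate, and section 8 states none. The only reference value is zero change.

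**Rejection rate when the drug does nothing.** The inputs are N = 12, two-sided 5%, an exact signed-rank test and normally distributed changes. The untreated mean fall and the SD of change are assumptions. Simulated chance of a significant improvement:

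| Assumed untreated mean fall | SD 2 | SD 3 | SD 4 |
|---|---|---|---|
| 0 | 2% | 2% | 2% |
| 1 point | 32% | 16% | 10% |
| 2 points | 85% | 51% | 31% |

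Rounding the changes to whole PDAI points gives about 30% and 16% for a 1-point fall (SD 2 and 3), and about 85% and 52% for 2 points. The test keeps its nominal error only in the first row. Every fall shown is below the protocol's own 3-point threshold.

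A sign test shows the same pattern without an SD. It needs 10 of 12 patients improved for two-sided 5%. The chance of that is 1.9% if 50% improve untreated, 8.3% at 60%, 25.3% at 70% and 55.8% at 80%.

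**Three-point responders when the drug does nothing.** On whole points, P(fall ≥ 3) = P(Z > (2.5 − mean)/SD):

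- Mean fall 0: (2.5 − 0)/2 = 1.25 gives 11%; (2.5 − 0)/3 = 0.83 gives 20%.
- Mean fall 1: 23% (SD 2), 31% (SD 3).
- Mean fall 2: 40% (SD 2), 43% (SD 3).

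Under these assumptions variability alone produces 11% to 20% responders. Only the excess over that comes from the assumed fall.

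**The interval that is tested.** Endoscopy and biopsies are done on Day 1 and again on Day 13 to 16, so those 12 of 18 points span 13 − 1 = 12 to 16 − 1 = 15 days. The clinical items (6 of 18) are less certain. Section 7 (Intervention) has a history and examination on Day 1, but the only pre-treatment data form with clinical PDAI items is the enrolment form (Appendix 3). The Day 1 form (Appendix 4) has endoscopic items only.

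**The forms.** The score-1 category for extra stools per day is 1–2 in Appendices 1 and 3, 1–3 in Appendix 7 and 1–4 in Appendix 8. The score-2 category is 3 or more in Appendix 1 and more than 3 in the others. A patient with 3 extra stools scores 2 by Appendix 1, fits neither category in Appendix 3, and scores 1 by the follow-up form in Appendix 8.

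**Carry-over to the next trial.** The sample size for comparing two means varies as 1/difference². Suppose Phase II shows a mean fall of 3 points of which 1 is untreated course. Planning on 3 instead of 2 makes the next trial too small by (3/2)² = 2.25. If 2 points are untreated course, the factor is (3/1)² = 9. These splits are assumptions.

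**The case against.** The strongest reply is that the protocol already states its limits. It is called a proof-of-concept study, declares a single open arm, defines the Phase II objective as a change in PDAI, disclaims a definitive answer on efficacy and looks ahead to a larger trial. Every uncontrolled pilot has this limitation. Much of that stands: the design is acceptable for its purpose, and no passage says that significance will be reported as proof of effectiveness. What remains is that section 8 still names testing effectiveness as the purpose, with significance as the criterion, and passes the result on without mentioning natural course.

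The reply is also right to rule out several stronger readings that a reader might infer:

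- *That the protocol's own definition shows flares settle untreated within 4 weeks.* It does not. The paired definition of chronic disease refers to therapy, so the cut-off may describe treated episodes. The formal inclusion criteria require only a diagnosis of pouchitis, not acute disease.
- *That the tested change runs over about 30 days*, by adding the two-week wait to Day 16. The wait comes before the Day 1 endoscopy. Settling during it lowers the endoscopic and histological baseline and does not inflate the change. Only the clinical items could span it.
- *That regression to the mean affects the whole score.* Endoscopy and histology are scored afresh on Day 1, after selection, which limits it for 12 of 18 points.
- *That the rejection rates above are the trial's false-positive rate.* They follow from assumed falls and SDs. The final test is also not named; section 8 leaves it to appropriate tests, and a statistical analysis plan not seen here may fix it.

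**Conclusion.** The point holds as a mismatch between section 8's stated purpose and what its comparison can show. A significant paired change is a change from baseline. With one arm and no benchmark, it cannot be attributed to the drug. The disclaimer in section 10 softens this but does not reach section 8 or the planned sample-size use.

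The size is unknown, because the documents give neither an untreated course nor an SD of change. As illustration only, an untreated mean fall of 1 point would give significance in about 16% to 30% of trials at N = 12, and 2 points in about 51% to 85% (SD 3 to 2; lower at SD 4). This assumes a two-sided signed-rank test at 5%. The documents do not support saying that spontaneous improvement of this size will occur, or that the trial needs a control arm to serve as proof of concept.

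**What to change.** 1. In section 8, restate the purpose of the 12 Phase II patients as estimating the change in PDAI after treatment. Add that p ≤ 0.05 shows change from baseline and not drug effect, in line with section 10 (Choice of study design). Note that the effect passed to future sample-size calculation includes natural course.
2. Report the change in PDAI and the 3-point responder proportion with 95% intervals, exact for the proportion. For scale, 8 of 12 responders gives 35% to 90%.
3. Score the clinical PDAI items on Day 1 before dosing, at the history and examination already planned, and use that score as the baseline in Appendix 7. First make the stool-frequency categories the same in Appendices 1, 3, 7 and 8.

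The clinical change from enrolment to Day 1 may be shown descriptively. It cannot serve as an untreated reference: it covers 6 of 18 points, and Appendix 2 places screening on Day 0 and baseline on Day 1, so it may be one day long.

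The cost is a few sentences in section 8, corrected forms and four items repeated on Day 1. No visit is added. The downside is a weaker headline claim.
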